14.2.2 Turnaround Time

Time from swab collection to result availability will be recorded in minutes for both the new POCT device and the established testing device. As both tests are conducted on the same participant, paired comparisons will be analysed using the paired t-test (or Wicoxon's if data are non-normally distributed). Mean (or median) differences will be reported with 95% confidence intervals and p-values.

14.2.3 Acceptability

Participants will complete a brief 'questionnaire' assessing the acceptability of the new POCT device including comfort and willingness to repeat the test. Responses will be collected using Likert scales and categorical items. Data will be analysed using descriptive statistics and comparisons with the standard test will be conducted using Wilcoxon's signed-Rank test using JASP software.

14.2.4 Cost Benefit Analysis

We will evaluate the health economic implications of using the new POCT device to detect two additional pathogens earlier in the patient's care pathway. In the current clinical pathway patients with negative results on the standard test and ongoing symptoms may undergo delayed or reflex laboratory testing to identify other infections, including pathogens targeted by the new test. By enabling earlier diagnosis and treatment at the point of care, the new test may reduce time to treatment, avoid unnecessary empirical therapies and improve resource utilisation. This component will be assessed through a within-trial cost effectiveness analysis using trial data to compare diagnostic pathways and estimate cost per additional case detected, cost per timely treatment initiated and incremental cost-effectiveness ratio (ICER).

The overall hypothesis is that the new test will demonstrate superior sensitivity for RSV based on preliminary data and known limitations of the current test and show the added benefits of the earlier diagnosis on the hospital costs and prescribing.

14.3 Sample Size Calculations

These calculations are based on the expected sensitivity/specificity and desired precision. Methods used are those described by Buderer (1996) and/or Bujang & Adnan (2016) for diagnostic test evaluation.

14.3.1 For Sensitivity (or Specificity)

$$n=(Z^2.P.(1-P))/d^2$$

n = number of diseased (or non-diseased) subjects required

Z = 1.96 for 95% confidence (the assumption is that this approach could apply to either sensitivity or specificity but here we expect sensitivity will require the higher resolution)

P = expected sensitivity (or specificity) (0.95) for two tailed test

d = desired precision (0.10)

Samples needed for positive cases (sensitivity):

n = 18.2 >>> 19 cases.

From our above table our minimum expected prevalence for any one type of disease is 5% and our maximum is 15% so we can easily estimate what sample total will most likely deliver 19 cases.

If prevalence is low:

N = n/prevalence = 19/.05 = 380 cases.

If the prevalence is uniformly high:

N = n/prevalence = 19/.15 = 127 cases.

This gives us a range of sample size which allows for this variable prevalence. If we assume the worst prevalence state, then 380 cases are required and a further 20 might provide additional safety to achieve a 19-event incidence for each type of infection.

Thus, the recommendation is for a trial recruiting **400** participants.

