9.0 STUDY OBJECTIVES

9.1 Primary Objective

The primary objective of the study is to demonstrate that the Logicore System multiplex 6 panel respiratory pathogens point of care testing device has increased diagnostic sensitivity when compared to the current gold standard POC multiplex panel at CUH Trust whilst maintaining accuracy, including Positive Predictive Value (PPV), Negative Predictive Value (NPV) and specificity.

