14.2 Study Endpoints

14.2.1 Specificity (or Sensitivity)

The Primary Endpoint is to demonstrate the sensitivity and diagnostic accuracy of the new Logicore System POCT device compared to the current gold standard (Cepheid) for the four overlapping infections. Based on an expected sensitivity of 95% and a 10% allowable margin, approximately 19 positive cases per infection are required to estimate sensitivity with a 95% confidence. Assuming a positivity rate of up to 50% based on the selection criteria, 400 patients will ensure sufficient numbers of true positive cases for each pathogen and enable accurate estimation of sensitivity, specificity and predictive values for both tests. The paired design allows for direct comparison of the new and established test results using McNemar's test and Cohen's Kappa.

As a secondary component we will evaluate turnaround time, patient and staff acceptability of the new test, and Cost-Benefits of the new test device.

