14.5 Statistical Methods

14.5.1 Primary Outcomes

The outcome data from each testing device will be compared against its paired standard to produce 2 x 2 tables for each type of disease

Disease +ve Disease -ve

	Standard positive	Standard negative
Test positive	True Positive (TP)	False Positive (FP)
Test negative	False Negative (FN)	True Negative (TN)

From this we calculate:

i. Sensitivity, Specificity

Sensitivity is the percentage of cases that had the observed outcome was correctly predicted by the model (i.e., TP/(TP+FN).

Specificity is the percentage of observations that were also correctly predicted as not having the observed outcome (i.e., TN/FP+TN).

- ii. Positive Predictive Value
- iii. Negative Predictive Value
- iv. Likelihood Ratios (LR+ / LR-) for the strength of the test versus standard
- v. Accuracy and Cohen Kappa (for agreement)
- vi. If data allows, we intend to model some ROC curves around the various clinical thresholds to ascertain the best use model for this device in this clinical setting.

These core calculations and tests will be performed using JASP software on the recorded data sets.

vii. McNemar's test to compare sensitivity/ specificity.

McNemar's test will be used to assess paired differences in positive and negative results between the new POCT and the established gold standard test for each of the four shared respiratory infections. This test focuses on cases where the two tests disagree, quantifying whether the new test detects significantly more or fewer positive results than the comparator.

For example, among patients tested for RSV, if the new test identifies more positive cases than the gold standard, and this difference is statistically significant on McNemar's test (p < 0.05), this may indicate **superior sensitivity**. Results will be reported with the test statistic, degrees of freedom, and p-value. A similar analysis will be repeated for each infection, supporting the primary endpoint of diagnostic accuracy.

McNemar tests the **null hypothesis** that both tests have the same proportion of positive results by evaluating a test statistic and comparing this with a Chi squared distribution statistic if the value is lower then the null hypothesis is proved.

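### The 400 is sized for the precision of one sensitivity estimate, but the primary question is paired superiority over Cepheid per pathogen, and a probable non-significant McNemar test would be read as proof of equality

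*Protocol*

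**What the plan says.** **Sizing.** Protocol 14.3 bases the calculation on expected sensitivity and desired precision. Section 14.3.1 obtains 19 positives per infection, divides by the lowest prevalence (5%, Flu B), and concludes: "If we assume the worst prevalence state, then 380 cases are required and a further 20 might provide additional safety". Section 14.2.1 adds that "400 patients will ensure sufficient numbers of true positive cases for each pathogen and enable accurate estimation of sensitivity, specificity and predictive values", and then says that the paired design permits a direct comparison by McNemar's test and kappa.

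**Objective.** Section 9.1 sets out to demonstrate that Logicore "has increased diagnostic sensitivity when compared to the current gold standard POC multiplex panel at CUH Trust whilst maintaining accuracy". Section 14.2.4 states: "The overall hypothesis is that the new test will demonstrate superior sensitivity for RSV based on preliminary data".

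**Analysis.** Section 14.5.1 applies McNemar's test to each of the four shared pathogens. Its RSV example says that if Logicore finds more positives and "this difference is statistically significant on McNemar's test (p < 0.05), this may indicate" superior sensitivity; the same analysis is repeated for every infection in support of the primary endpoint. The test is described as "evaluating a test statistic and comparing this with a Chi squared distribution statistic", and the section adds that a value below the reference proves the null hypothesis. The estimand table (14.6) gives the difference in sensitivity and specificity, with McNemar's test, as the primary summary measure.

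**The concern.** A precision formula controls the width of the interval around one proportion. It contains no comparator, no target difference and no power. A McNemar comparison depends only on pairs in which the devices disagree, and 20 to 60 infected participants per pathogen supply few of those.

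Two things are at stake. A real advantage of moderate size would probably be missed for most pathogens. And because 14.5.1 equates a low statistic with proof of the null, that miss would be reported as a positive finding that the devices are equally sensitive.

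**Working it through.** **1. The plan's own figure.** n = Z²P(1−P)/d² = 1.96² × 0.95 × 0.05 / 0.10² = 18.2, rounded up to 19. Then 19/0.05 = 380, and 380 + 20 = 400. This reproduces. Nothing in it refers to Cepheid's sensitivity or to discordance.

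**2. Expected infected participants in 400**, from the prevalence table in 14.1: Flu B 5% = 20; Flu A 10% = 40; SARS-CoV-2 10% = 40; RSV 15% = 60; sum 160.

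**3. Assumptions the protocol does not supply.** Logicore sensitivity is 0.95 (the sizing input). Cepheid sensitivity sC is 0.90 or 0.85. True infection status is taken as known and only infected participants are counted. Let p10 be the probability that only Logicore detects an infected case, and p01 that only Cepheid does. The two extremes considered are:

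- Independent misses: p10 = 0.95(1 − sC), p01 = 0.05 sC. At sC = 0.90 these are 0.095 and 0.045.
- Fully nested misses (Logicore detects everything Cepheid detects): p10 = 0.95 − sC, p01 = 0. At sC = 0.90 this is 0.05 and 0.

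**4. Why power is low.** With b Logicore-only and c Cepheid-only positives, the statistic is (b − c)²/(b + c), compared with 3.84. With c = 0 the uncorrected test needs b = 4 (16/4 = 4.0); the exact test needs b = 6 (2 × 0.5⁶ = 0.031, whereas b = 5 gives 0.0625). With c = 1, 2 or 3 the uncorrected test needs b = 7, 9 or 11. At a 5-point gap with nested misses, the expected b is only 0.05 × 20 = 1, 0.05 × 40 = 2 and 0.05 × 60 = 3.

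**5. Power**, by enumerating all values of b and c and counting two-sided p < 0.05 in Logicore's favour (uncorrected chi-square / exact):

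| Cepheid sensitivity, overlap | Flu B, 20 | Flu A or SARS-CoV-2, 40 | RSV, 60 | Pooled, 160 |
|---|---|---|---|---|
| 0.90, independent | 5.3% / 0.4% | 12.0% / 4.4% | 15.7% / 9.3% | 41% / 32% |
| 0.90, nested | 1.6% / 0.03% | 13.8% / 1.4% | 35.3% / 7.9% | 96% / 82% |
| 0.85, independent | 15.1% / 2.9% | 29.5% / 18.0% | 42.6% / 33.0% | 87% / 81% |
| 0.85, nested | 13.3% / 1.1% | 57.7% / 20.6% | 86.3% / 56.3% | >99% / >99% |

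Partial overlap does not change the picture: at sC = 0.90 the 40-case chi-square figure peaks at about 15%.

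**6. What 80% power would take.** For a 5-point gap, the normal-approximation formula n = [1.96√(p10 + p01) + 0.84√(p10 + p01 − δ²)]²/δ², with δ = p10 − p01 = 0.05, gives about 438 infected cases per pathogen (independent) or 155 (nested), against 20 to 60 expected. Conversely, repeating the enumeration in whole-point steps, the smallest gap with 80% power, over both overlaps and both test forms, is about 26 to 42 points for Flu B, 14 to 26 for Flu A and SARS-CoV-2, and 9 to 19 for RSV.

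**The case against.** The strongest reply is that the protocol never claims power for superiority. Section 14.3 openly sizes on precision, 10.1 frames the endpoint as measurement, and 14.1 describes the study as mainly validating performance. The reassurance in 14.2.1 concerns estimation; its next sentence says that the paired design permits a comparison, not that 400 is powered for one. This stands, and it limits the point. A reader might infer that p < 0.05 for each pathogen is a formal success rule and that the study fails without it. The documents do not say so: 14.5.1 introduces the threshold as an example and says only that it may indicate superiority. What remains is that 9.1 sets a superiority objective and no other criterion for judging it is given.

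A second reply is that any single power figure is arbitrary. Cepheid's sensitivity and the overlap of misses are not stated, nor is a continuity correction. This also stands, which is why ranges are given. A reader might infer that non-significance is likely for every pathogen even at a 10-point gap. That is not supported: with nested misses and the uncorrected test, RSV reaches 86% and Flu A and SARS-CoV-2 reach 58%. RSV is also the one pathogen for which 14.2.4 names a superiority hypothesis. The lower detection limit expected in 7.1 would push misses towards nesting, although separate swabs from each nostril work against complete nesting.

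A third reply is that a pooled test sits badly with 14.1, which wants the sensitivity goal met for each pathogen. That is why it should be an addition and not a substitute.

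**Conclusion.** The point holds as a mismatch between the basis of the sample size and the primary comparison, made worse by the interpretation rule. At a 5-point gap no pathogen exceeds about 35% power under any overlap or test form tried. At 10 points Flu B stays at about 15% or below, and RSV is adequately powered only with largely nested misses and the uncorrected test. A non-significant result would therefore usually be uninformative, yet 14.5.1 would have it read as proof that the tests are the same.

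The percentages rest on the assumed Cepheid sensitivity, Logicore at 95%, the prevalences in 14.1, known infection status and full recruitment with no invalid samples. The mismatch itself rests on none of these. It does not follow that 400 is the wrong number for an estimation study, or that more patients are required.

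**What to change.** 1. In 14.2.1 and 14.3.1, state that 400 was chosen for the precision of each pathogen's sensitivity estimate and is not powered for per-pathogen superiority. Print the detectable differences at 20, 40 and 60 cases as a range, with the assumptions beside them.
2. In 9.1, 14.5.1 and 14.6, make the per-pathogen primary result the paired difference with its 95% CI and treat the per-pathogen McNemar tests as supportive. Replace the statement that the null hypothesis is proved with one saying that the tests were not shown to differ.
3. Optionally, alongside the per-pathogen results, prespecify one paired test pooled over the four shared pathogens for the panel-level objective in 9.1. It would use about 160 positives, with co-infections clustered by participant. State its power: about 32 to 96% at a 5-point gap and 81% or more at 10 points, before any allowance for clustering.

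The cost is protocol wording only; enrolment and procedures do not change. The downside is that per-pathogen superiority is no longer presented as something the study is sized to show, and a pooled result speaks for the panel and not for any single pathogen.

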14.3.2 Turnaround Time

Time from swab collection to result availability will be recorded in minutes for both the new POCT and the established testing device. As both tests are conducted on the same participant, paired comparisons will be analysed using the paired t-test (or Wilcoxon's if data are non-normally distributed). Mean (or median) differences will be reported with 95% confidence intervals and p-value.

14.3.3 Patient Acceptability

Participants will complete a brief questionnaire assessing the acceptability of the new POCT including comfort and willingness to repeat the test. Responses will be collected using Likert scales and categorical items. Data will be analysed using descriptive statistics, and comparisons with the standard test will be conducted using Wilcoxon's signed-Rank test using JASP software.

14.3.4 Cost Effectiveness Analysis

We will be using real patient data on those who fail the original test but are positive on the new test device and have ongoing symptoms requiring further hospital activity and

testing. Potentially some may spontaneously improve after the first test and be lost to this analysis.

The data may consist of individual measures of Length Of Stay (LOS), complications, time to treatment etc.

$$n = \left(rac{(Z_{1-lpha/2} + Z_{1-eta}) \cdot \sigma}{\Delta}
ight)^2$$

The sample size depends on:

 σ = the SD of the effect or costs

 Δ = minimally important clinical difference.

For example: cost saving £500 with an SD of £1000 then n = 31.4 or a requirement of 32 per group to analyse.

If we argue that a maximum of 5% of cases will fail the standard test but be positive on the new test and reflex test, then at around 400 patients total we should hope to see 20 - 25 patients per extra infection which is enough to evaluate impact meaningfully.

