14.0 STATISTICAL ANALYSIS PLAN

14.1 Rationale

According to the Office of National Statistics report on the results of the 2021 Census⁷, the population of Cambridge is approximately 146,000 people. Of this population, around 75% classed their ethnicity as White (comprising the following categories: British, Irish, Roma, Gypsy or Irish Traveller, or Other) and around 15% are children aged 15 years or less. For this clinical study, it is expected approximately 20% of participants will be less than 16 years of age, and the majority of participants will be white Caucasian, providing a casemix with external validity in line with the demographics of the catchment area.

This prospective paired diagnostic accuracy and economic evaluation study is designed to assess the clinical performance and potential health system impact of a new molecular Point Of Care Test for respiratory infections in the Emergency Department (ED) setting. The new Logicore System testing device detects six key respiratory pathogens including four infections currently targeted by the current gold standard test (Cepheid); Influenza A (Flu A), Influenza B (Flu B), Respiratory Syncytial Virus (RSV) and SARS-CoV-2. The Logicore System device detects two additional pathogens not included in the established POCT; *Mycoplasma pneumoniae* (MP) and human adenovirus (HAdV).

During the winter season planned for this study, the overall positivity of the current POCT for respiratory disease is estimated at 30-50% of those selected by the respiratory criteria for the standard test (CUH personal communication). However, it is recognised that infections do not distribute evenly by age, or season, or time of the season. For example, RSV is more common in the very young or elderly and has peaks later in the winter months. Thus, the statistical approach to assessment requires us to estimate how many true positives per infection type* might be expected to achieve a sensitivity of 95% with a 10% margin of error, not just overall.

Also, during the winter season, disease type incidence will occur in runs and hence it is possible to inadvertently populate the whole study with one type of infection.

Logically our total sample size will need to be calculated on the lowest prevalence infection. As this is planned as an Intention To Treat study (ITT), i.e. including clinical benefits, then 10-15% extra samples would provide a reasonable margin of samples to allow for withdrawals and invalid samples.

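### Section 14.3.4 takes its economic data only from Cepheid-negative/Logicore-positive patients whose symptoms persist, which overstates the mean saving per extra detection and distorts the ICER in an undetermined direction

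*Protocol*

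**What the plan says.** Section 14.2.4 sets the economic aim. Trial data will be used to "compare diagnostic pathways and estimate cost per additional case detected, cost per timely treatment initiated and incremental cost-effectiveness ratio (ICER"). None of these outputs is limited to patients who stay ill. Section 14.5.4 proposes a simple decision tree for the two pathways and stresses that the new device gives its answer at first presentation.

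Section 14.3.4 then names the patients whose data will be used: "those who fail the original test but are positive on the new test device and have ongoing symptoms requiring further hospital activity and" testing. The next sentence accepts the consequence: "Potentially some may spontaneously improve after the first test and be lost to this analysis".

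The same section gives a sizing example ("cost saving £500 with an SD of £1000 then n = 31.4 or a requirement of 32 per group to analyse") and a yield estimate based on a "maximum of 5% of cases will fail the standard test but be positive on the new test and reflex test".

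Two other places bear on the point. Sections 14.2.4 and 14.5.4 locate delayed or reflex testing, and its effect on stay and care, in patients who are negative on the standard test and remain symptomatic. Section 11.0, item C, has the second-line swab taken only if symptoms persist, and classes a Logicore positive that does not match the second-line result as a false positive.

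**The concern.** Persistence of symptoms is known only after the Logicore result. Selecting on it changes the question from what is saved per extra detection when the test is used at presentation to what is saved among those extra detections who later stayed ill. The test cannot be used only on that second group, because it cannot be recognised at presentation.

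The selection is not neutral. A patient who improves unaided has little or no reflex test or extra stay to avoid, yet is still an extra Logicore positive and may have been treated on it (section 8.2 allows that such a result may bring treatment forward). The patients left out are thus those with least to save. At stake is the cost-benefit result, a named secondary objective that section 7.1 says will be provided to the Trust.

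**Working it through.** **1. The plan's own figure.** The formula in 14.3.4 is n = ((Z₁₋α/₂ + Z₁₋β)·σ/Δ)². Inputs from the section are Δ = £500 and σ = £1000. Alpha and power are not given as numbers there; two-sided 5% and 80% power are assumed.

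n = ((1.960 + 0.842) × 1000/500)² = 31.4, rounded up to 32. The stated figure reproduces. The £500 is used below only as an example of the saving in retained patients.

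**2. Mean saving per extra detection.** Let s be the share of Cepheid-negative/Logicore-positive participants who improve, and h their mean saving. Neither is in the documents; both are assumptions.

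Mean over all extra detections = (1−s) × £500 + s × h. 
Overstatement = £500 / that mean − 1. With h = £0 this is 1/(1−s) − 1.

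| s | h = £0 | h = £250 | h = −£50 |
|---|---|---|---|
| 10% | £450; 11% too high | £475; 5% | £445; 12% |
| 25% | £375; 33% | £437.50; 14% | £362.50; 38% |
| 50% | £250; 100% | £375; 33% | £225; 122% |

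With h = £0 the overstatement reaches 10% at s = 1/11, about 9%. It vanishes at h = £500 and reverses only if improvers save more than those who stay ill: at h = £700 the restricted figure is 0.96 of the full mean for s = 10% (500/520) and 0.83 for s = 50% (500/600). The pathway described in the protocol gives no reason to expect that.

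**3. Cost per additional case detected.** Purely illustrative inputs: 400 tested, £20 extra test cost each (assumed), 20 extra detections, 10 of whom improve with no saving, and £500 saved in each of the other 10.

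- Net cost = 400 × £20 − 10 × £500 = £8,000 − £5,000 = £3,000, with or without the improvers.
- Restricted count: £3,000/10 = £300 per case. Full count: £3,000/20 = £150 per case. Here the restriction works against Logicore.
- If instead the restricted £500 were applied to all 20 detections, net cost would be £8,000 − £10,000 = −£2,000, an apparent saving in place of a £3,000 cost. Here it works in favour of Logicore.

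The protocol does not say which calculation will be made, so the direction for the ICER is open.

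**4. Does the decision tree repair this?** The inputs in 14.5.4 include a general line for the probabilities of infections and outcomes. No branch for spontaneous improvement is named, and 14.3.4 says the patient data will lack these people.

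**The case against.** The best defence is one of place. Section 14.3.4 sits under sample size; the method is in 14.5.4, where a decision tree could weight persistence by its probability and use patient-level costs only on the branch where reflex costs arise. Branch detail is often left to a later plan, and the sentence about improvers can be read as an admitted limitation. This stands in part: such a tree would remove the bias in the mean saving. But 14.3.4 states a data source, not just a sizing assumption, and a tree cannot cost its improver branch from data that were not kept.

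Four stronger readings are tempting and are not supported.

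- *That every economic output is tilted towards Logicore.* Step 3 shows that cost per additional case can move either way; only the mean saving per extra detection has a clear direction.
- *That Logicore positives not confirmed by the reflex test are also dropped.* The reflex-positive condition appears only in the yield estimate ("a maximum of 5% of cases will fail the standard test but be positive on the new test and reflex test"). The sentence defining the data has no such condition.
- *That this breaks an intention-to-treat commitment.* The wording in 14.1 ("As this is planned as an Intention To Treat study (ITT), i.e. including clinical benefits") introduces an allowance for withdrawals and invalid samples. It does not define the economic population.
- *That the result will decide adoption.* Section 7.1 says only that the Trust will be given a cost-benefit analysis.

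**Conclusion.** The concern holds for the mean saving per extra Logicore detection. As written, 14.3.4 selects on an outcome that follows the test, and 14.2.4 and 14.5.4 ask a question that starts at presentation. The overstatement is 1/(1−s) if improvers save nothing: 11% at s = 10%, 33% at s = 25%. It is smaller if improvers save something. The direction rests on improvers saving less than those who stay ill, which follows from the pathway the protocol describes but is not shown by data in it. The size cannot be derived from the documents, because s is not given and £500 is only a sizing example.

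Cost per additional case detected and the ICER are distorted too, without a determined direction, since improvers drop out of the effect count as well as the cost side.

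**What to change.** In 14.3.4 and 14.5.4:

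- Include downstream costs and outcomes for every Cepheid-negative/Logicore-positive participant, whatever their later symptoms, and delete the clause accepting that improvers are lost.
- Add an explicit branch for improvement to the decision tree, with its probability and costs taken from the trial.
- Let unconfirmed Logicore positives contribute their costs, but do not count them as additional true cases where section 11.0, item C, classes them as false positives.
- Report improvers without a second-line result as unverified, and show the result both counting and not counting them as cases.
- Keep the persisting-symptom result, if wanted, as a labelled subgroup.

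The cost is wording plus the same record extraction for more patients. For every 20 retained patients, 20·s/(1−s) improvers are added: about 2 at s = 10%, 7 at 25%, 20 at 50%. Section 11.0 already collects admission, discharge diagnosis and mortality to 30 days for all participants. Length of stay and costs are not on that list and must be extracted for the retained group anyway. The stated saving per detection will probably be smaller.
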